5 STUDY PROCEDURES

The study will ensue in two phases: phase 1 – training set, and phase 2 prospective trial.

The first 20 patients undergoing US-DOT will comprise the training set to accomplish the aims of:

- 1) assessing US-DOT data,
- 2) assessing intra-observer variability in the assessment of US-DOT data
- 3) assessing inter-observer variability in the assessment of US-DOT data.

For phase 2, the prospective trial, up to 315 patients will be recruited with the expectation that approximately 5% will not successfully complete the study so that 300 patients will have valid US-DOT data for the ensuing reader study.

The study flow chart that integrates US-guided DOT collection into the standard of care (SOC) clinical workflow is shown below (figure 3). SOC clinical workflow includes review of patient information and diagnostic information, such as conventional imaging results with BIRADS

[figure not shown]
assessments. The study coordinator will approach eligible patients prior to biopsy to assess their willingness to participate in the study. Patients that are willing to participate will sign informed consent and undergo US-guided DOT imaging before biopsy. A subset of patients will also undergo CEM.

Breast radiologist coinvestigators will perform (or supervise certified breast US technologists) in all NIR/US studies. As noted above, they will not be blinded to any clinical data. The function of the imaging specialist in US guided DOT imaging is to ensure that the correct anatomic location of the index lesion is imaged.

[figure not shown]
The study radiologist that performs/supervises the US-guided DOT imaging will complete CI and US-guided DOT case report forms (CRFs) blinded to the pathology result of the ensuing biopsy. In the event that the patient also undergoes CEM the study radiologist will complete CI and CEM CRFs blinded to the pathology result of the ensuing biopsy. Details of CRF completion and related reader study are noted in section 7 – Data Collection and Analysis below.

Figure 3. Study work flow

Training Set:

Prospective Trial

6. US and OPTICAL IMAGING

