Up to 315 participants will be enrolled to yield 300 participants with valid US-DOT data to evaluate the primary and secondary objectives as below.

Aim 1.1 Assess the impact of US-guided DOT on potential reduction of benign biopsies
The primary objective of this prospective study is to assess the impact of US-guided DOT on the potential reduction of benign biopsies, a.k.a, improve specificity. We hypothesize that the adjunctive use of US-guided DOT will reduce the rate of benign breast biopsy. Using these criteria, the first endpoint, specificity = $Gd/(Gb+Gd)$, will be calculated as the proportion of subjects with a negative assessment (BI-RADS 2 or 3) and with no cancer at biopsy. With the exception of a small minority of patients with BI-RADS 3 assessments who elect to undergo biopsy and who will be tracked separately, all subjects in this study are considered positive using the current SOC, because they have been recommended for biopsy. Hence, 1) the specificity in this group for the SOC is 0% by definition; 2) the estimate of specificity for the DOT system represents the improvement in specificity; and 3) the estimate of specificity is also an indication of the percentage of benign biopsies that might be avoided if the NIR data were used by the radiologist in the biopsy decision making process.

Aim1.2 Assess the impact of US-guided DOT as an adjunct to CI on maintaining high sensitivity
To also ensure that the potential for false negatives is not a significant risk with the use of the US-guided DOT, we will also assess the probability of potentially misclassifying a malignant abnormality. By definition, $FN=Gc/(Gc+Ga)$, which is 1 minus sensitivity. Our earlier study [Zhu reference] indicated that both radiologists reached 96.6% to 100% sensitivity with the tHb data included, and therefore had a 0-3.4% probability of missing a malignant lesion.

All CRFs including CI, DOT, CEM and biopsy results will be entered by our study radiologists, or study coordinator or study pathologist into the OnCore data base to be exported to [name] for statistical analysis. An ad hoc analysis of the CI, CEM and optical imaging characteristics and histopathologic features of false negative cases will be performed to identify suspicious features that always indicate a level of suspicion warranting biopsy.

Aim1.3 Explore the potential benefit of managing post biopsy BI-RADS 4C and 5 lesions

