Study Hypothesis 1 for aim 1.1: The first hypothesis is that the measured tHb distribution and values can be potentially used as an adjunct for radiologists to reduce unnecessary biopsies in low risk patients with benign pathological results. The benign biopsy spare rate can be calculated as $Gd/(Gb+Gd)$ in Fig.11, which is equivalent to the specificity, the primary endpoint of Aim1.1. We observed in previous studies that specificity could be improved by 45% on average if NIR data were used in the decision-making process. Note that the specificity in this group of biopsied patients under the SOC is 0% by definition. In this study, we conservatively set the minimum acceptable specificity at 30%. The null and alternative hypotheses, which demonstrate superiority when the NIR imaging data are used as an adjunct to the diagnostic assessment versus when the SOC diagnostic data are used alone, are given by

$$H_0: \text{Specificity} \leq 30\% \text{ versus } H_1: \text{Specificity} > 30\%$$

This aim will be considered a success if the lower limit of the 95% confidence interval on specificity exceeds 30%. This hypothesis will be tested at the one-sided 0.025 level, rather than 0.05, to account for the fact that two hypothesis tests (on specificity and sensitivity) are planned. This aim is considered a success if the lower limit of the 97.5% confidence interval on specificity exceeds 30%.

Study Hypothesis 2 for aim 1.2: The second hypothesis is that, while reducing unnecessary benign biopsies, the addition of adjunct information from US-DOT still maintains a high sensitivity

in capturing nearly all malignant tumors. This can be evaluated based on sensitivity, which is calculated as $G_a/(G_a+G_c)$, as shown in Fig.11.

H_0 : sensitivity $\leq 90\%$ versus H_1 : sensitivity $> 90\%$

Based on previous study, we anticipate the sensitivity will be in the range of 96-100%. This aim is considered a success if the lower limit of the 95% confidence interval for sensitivity is at least 90%. This hypothesis will be tested at the one-sided 0.025 level, rather than 0.05, to stringently account for the fact that two hypothesis tests (on specificity and sensitivity) are planned. This aim is considered a success if the lower limit of the 97.5% confidence interval for sensitivity is at least 90%.

10.3 Sample size justifications.

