We expect ~300 eligible women who will undergo SOC biopsy with valid US-DOT data and fall in the BIRAD categories of 3, 4A, 4B, 4C, or 5, rendering ~210 pathologically benign biopsies and 90 malignant biopsies. **For Study Hypothesis 1**, prior study results indicate the specificity was estimated to be no less than 45%. A total of 83 benign biopsies are needed to achieve 80.18% power to test Study Hypothesis 1 at a 2.5% level. This calculation is based on a 1-sided exact binomial test by conservatively assuming the true specificity is 45%, while 210 benign biopsies achieve 99.4% power to test Hypothesis 1. We also calculated the sample size based on the more stringent requirement that the lower limit of the 1-sided 97.5% conservative Clopper-Pearson binomial exact confidence interval (CI) (60) to the estimated specificity (of 45%) should exceed 30%. The 210 benign biopsies will allow us to estimate the 1-sided 97.5% exact CI to be between 37.7%~100%, thus satisfying this more stringent requirement. **For Study Hypothesis 2**, 90 malignant biopsies will achieve 89.33% power to conduct Study Hypothesis 2 at a 1-sided 2.5% level, based on a 1-sided exact binomial test. With 90 malignant biopsies, the sensitivity can be estimated at 98% with a 1-sided 97.5% exact CI of 92.06%~100%, thus satisfying the stringent criterion requiring a lower limit of >90%.

In calendar year 2016, over 7,000 women came to the Siteman Cancer Center at WashU for diagnostic evaluation. Approximately 17% had suspicious or highly suggestive malignancy findings and were recommended for tissue sampling. Over 700 women underwent US guided biopsy, which is more than 10 times larger than the potential study subjects each year.

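### Does the 89.33% power for the sensitivity hypothesis need a guaranteed number of malignant lesions and a named alternative?

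*Combined protocol and SAP*

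**What the plan says.** Section 10.3 expects about 300 women with valid exams, "rendering ~210 pathologically benign biopsies and 90 malignant biopsies", which is a malignancy rate of 90/300 = 30%. From this it derives the power for Study Hypothesis 2 (null: sensitivity at most 90%; one-sided 0.025; exact binomial test): "90 malignant biopsies will achieve 89.33% power to conduct Study Hypothesis 2 at a 1-sided 2.5% level". The next sentence moves to precision and says that "the sensitivity can be estimated at 98% with a 1-sided 97.5% exact CI" lying above 90% would result.

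On the sensitivity to expect, 10.2 says "we anticipate the sensitivity will be in the range of 96-100" per cent. Aim 1.2 in 7.1 reports that in the earlier study "both radiologists reached 96.6% to 100% sensitivity with the tHb data included".

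Accrual is set in participants. Section 7.1 says "Up to 315 participants will be enrolled to yield 300 participants with valid US-DOT data", and section 5 says "up to 315 patients will be recruited with the expectation that approximately 5% will not successfully complete the study". No section sets a minimum number of malignant lesions. On the supply of patients, 10.3 notes for 2016: "Over 700 women underwent US guided biopsy". It adds that this is over ten times the number of potential study subjects per year.

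**The concern.** Three features together make the 89.33% look fragile.

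- **The alternative is not named.** For Hypothesis 1, section 10.3 says outright that it assumes 45% specificity. For Hypothesis 2 the power sentence names nothing, and 98% turns up only as a precision example. The plan's own range goes down to 96%, where power is much lower.
- **The lesion count is random.** Accrual ends on exams, so the number of malignant lesions will vary around 90, and 10.3 gives no source for the 30% rate.
- **The exact test moves in steps.** With 85 to 99 malignant lesions the test passes with up to 3 missed cancers; with 70 to 84 it passes with at most 2. A small shortfall could therefore cost a visible amount of power.

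At stake is the conclusion on sensitivity. If a reading strategy with true sensitivity well above 90% failed this test by chance, the specificity result would stand without its companion finding that cancers are not being missed.

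**Working it through.** **Inputs.** Null sensitivity 90%, one-sided 0.025 and the anticipated 96–100% (10.2); exact binomial test with Clopper-Pearson limit (10.4); 90 malignant among 300 (10.3); 96.6% as the low end of the earlier study (7.1). One call per lesion is assumed, as 10.3 does.

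**Rule.** With n malignant lesions, the allowed number of misses c(n) is the largest c with P[Bin(n, 0.10) ≤ c] ≤ 0.025. Power at true sensitivity S is P[Bin(n, 1 − S) ≤ c(n)].

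**Reproducing the plan's figure.** At n = 90, P[Bin(90, 0.10) ≤ 3] = 0.0169 and P[Bin(90, 0.10) ≤ 4] = 0.0465, so c = 3. At S = 0.98, the probabilities of 0, 1, 2 and 3 misses are

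0.16231 + 0.29812 + 0.27074 + 0.16208 = 0.89325, i.e. 89.33%.

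Other alternatives do not give this figure: 97.5% gives 81.1% and 98.5% gives 95.3%. The calculation therefore used 98%, the midpoint (96 + 100)/2 of the anticipated range.

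**Power by lesion count and sensitivity.**

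| Malignant n | Misses allowed | Attained alpha | 96% | 96.6% | 97% | 98% | 99% |
|---|---|---|---|---|---|---|---|
| 70 | 2 | 0.0242 | 46.6% | 57.3% | 64.9% | 83.5% | 96.7% |
| 75 | 2 | 0.0161 | 41.9% | 52.9% | 60.8% | 81.0% | 96.0% |
| 84 | 2 | 0.0077 | 34.2% | 45.3% | 53.7% | 76.3% | 94.8% |
| 85 | 3 | 0.0245 | 55.7% | 67.2% | 74.8% | 90.9% | 98.9% |
| 90 | 3 | 0.0169 | 51.3% | 63.4% | 71.5% | 89.3% | 98.7% |
| 99 | 3 | 0.0085 | 43.8% | 56.4% | 65.4% | 86.3% | 98.2% |
| 100 | 4 | 0.0237 | 62.9% | 74.6% | 81.8% | 94.9% | 99.7% |

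The step between 84 and 85 is real, but it belongs to the usual sawtooth of an exact test. At 98%, 85 lesions give more power than 90, and 70 give more than 84. Falling short of 90 is therefore no loss in itself; at 98% the loss begins below 85.

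**Letting the count vary.** Take M ~ Binomial(300, 0.30) and re-derive the rule at each M. Then P(M < 90) = 47.8%, made up of 23.3% at 85–89, where power is slightly above the stated figure, and 24.6% below 85. Average power at 98% splits as follows:

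- M < 85: probability 0.2456, mean power 0.7808
- M from 85 to 99: probability 0.6381, mean power 0.8882
- M ≥ 100: probability 0.1163, mean power 0.9434

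0.2456 × 0.7808 + 0.6381 × 0.8882 + 0.1163 × 0.9434 = 0.868.

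The random count thus costs 89.3 − 86.8 = 2.5 points. Even in the quarter of trials with fewer than 85 lesions, power averages 78%. On the same basis, average power is 48.1% at 96%, 60.0% at 96.6%, 68.2% at 97% and 97.9% at 99%.

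**A lower malignancy rate, as an assumption.** At 27.5%, average power at 98% is 82.5%; at 25% it is 77.1%. The only such rate in the document, just over 25% in section 1.1, refers to screen-detected abnormalities recommended for biopsy. This trial enrols ultrasound-visible lesions up to BI-RADS 5, so the rate does not carry over.

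**Price of guaranteeing the count.** One hundred malignant lesions at a 30% rate need 100/0.30 ≈ 333 valid exams, or 333/0.95 ≈ 351 enrolled, against the cap of 315. The statement in 10.3 implies fewer than about 700/10 = 70 potential subjects a year, hence fewer than about 5 × 70 = 350 over the five funded years named in section 2.

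**The case for a change.** The strongest case for a change rests on the low end of the plan's own range. If true sensitivity is 96.6%, as in the less favourable result of the earlier study, a trial with a random count at the 30% rate fails about 40% of the time (100 − 60.0) although sensitivity is well above 90%. Section 10.3 describes its specificity assumption as conservative and makes no such claim for 98%, so 89.33% gives more comfort than the lower half of the range supports. Stopping on the malignant count would also be valid: it comes from pathology without reader calls and leaves the test and its level untouched.

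The arithmetic of this case stands, and so does the remark that the power sentence should have carried its alternative. The remedy does not follow. The plan sets no target of 80% power at 96.6%, and looking only at the lower half leaves out 98.7% at 99% and certain success at 100%. A floor of 85 lesions would remove the step but still give only 67.2% at 96.6% with 85 lesions, so it would not reach the weak spot. Reaching 80% there takes 114 lesions: 114/0.30 = 380 valid exams, or 380/0.95 = 400 enrolled. That is beyond the accrual the plan itself considers feasible. Nor does low power weaken protection of patients: the chance of passing when sensitivity is 90% or less stays at or below 0.025 at every lesion count. The error at issue is a missed claim of success.

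**Conclusion.** No change is needed. The 89.33% is right for 90 malignant lesions and 98% sensitivity, and allowing for a random count at the planned 30% rate leaves 86.8%. The unnamed alternative is a drafting gap that a reader fills from the following sentence of 10.3. Naming it would alter no result, because the analysis applies the exact test to whatever count arises. Sizing at the midpoint of the anticipated range, with accrual fixed in participants, is a fair trade-off between power at the low end and more patients in a trial with limited yearly accrual.

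This rests on three assumptions: the plan's 30% malignancy rate, independent lesions with one call each, and 98% as a reasonable central value. If the rate were 25%, average power at 98% would be 77.1%. If sensitivity were 96%, 90 lesions would give 51.3%. Someone reading a failed Hypothesis 2 should keep those figures in mind, since such a failure would not by itself show that sensitivity is 90% or less.

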10.4 Data Analysis

All data will be analyzed as it is without imputations. Summary statistics will be used to summarize data including mean, median, standard deviation, interquartile range for continuous data and count (percentage) for categorical data.

All evaluable subjects will be analyzed. In addition to the specificity and sensitivity of US-guided DOT results, PPV, NPV, and overall accuracy will be calculated. The two study hypotheses will be tested by a binomial exact test and by constructing the one-sided 97.5% Clopper-Pearson exact confidence intervals for specificity and sensitivity. The lower limit will determine the achievement of study goals. We will explore the data further to refine the classification algorithm and the cut-off threshold. ROC analysis will evaluate the quantitatively measured tHb for pathological results of malignant biopsies. Besides tHb and its distribution, other parameters (such as oxyHb, deoxyHb, and distributions) will be either linearly incorporated with tHb to maximize the ultimate area under ROC or non-linearly through a tree-based classification model (e.g., using the R package “rpart”) (62).

The area under the ROC will be calculated to gauge the model's overall discriminative ability for biopsy results.

For the exploratory study (discordant biopsy results), the imaging data (e.g., tHb, oxyHb etc) will be summarized as appropriate in the subset of participants whose BIRAD results yield highly suspicious abnormalities (BI-RAD 4C, 5) but pathology yield benign results. Two sample t-test or Wilcoxon rank sum test as appropriate will be applied to compare this subset versus those with a malignant biopsy.

For the exploratory Study (CEM DOT correlation), we will compare BI-RADS assessments of CI&CEM vs. CI&US-guided DOT as well as correlate imaging data such as intensity of enhancement in CEM and the total hemoglobin level of US-DOT using Pearson or Spearman correlation coefficients. We will evaluate concordance/disconcordance between US-guided DOT and CEM using agreement measure (Kappa coefficient) and will test the discordance using McNemar test.

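### Specificity is estimated only in participants with valid US-DOT data but read as the percentage of benign biopsies avoidable; failed scans, who would still be biopsied, are left out, so that percentage is somewhat overstated

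*Combined protocol and SAP*

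**What the plan says.** Section 5 recruits up to 315 for the prospective phase, expecting that "approximately 5% will not successfully complete the study so that 300 patients will have valid US-DOT data". Section 7.1 evaluates the primary and secondary objectives in those 300, and section 10.3 takes its roughly 210 benign and 90 malignant cases from them. Section 10.4 adds "All evaluable subjects will be analyzed" and rules out imputation. Evaluable is not defined, and no rule says how a failed or uninterpretable scan counts.

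The endpoint carries two meanings. In section 10.2, "The benign biopsy spare rate can be calculated as $Gd/(Gb+Gd)$ in Fig.11, which is equivalent to the specificity". In section 7.1 (Aim 1.1), "the estimate of specificity is also an indication of the percentage of benign biopsies that might be avoided". The same paragraph sets the baseline: apart from a few BI-RADS 3 patients who choose biopsy and are tracked separately, every participant counts as positive under standard of care because biopsy has been recommended.

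**The concern.** Specificity among usable scans and the share of benign biopsies avoided are the same number only if every scan is usable. A participant with a benign lesion and no valid DOT result gives the radiologist nothing on which to downgrade. She belongs in the denominator of a spare rate and cannot enter its numerator. The planned set leaves her out of both.

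For specificity and the spare rate the omission can only push the figure up. At stake are the headline percentage and, near the 30% bound, whether a result that meets the bound among valid scans would also meet it among the benign cases enrolled.

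**Working it through.** **Inputs from the documents.** Bound: "we conservatively set the minimum acceptable specificity at 30"% (10.2). Level: "This hypothesis will be tested at the one-sided 0.025 level" (10.2). Method: an exact binomial test and "constructing the one-sided 97.5% Clopper-Pearson exact confidence intervals for specificity and sensitivity" (10.4). Planning value: "conservatively assuming the true specificity is 45"% (10.3). Benign cases with valid scans: about 210 of 300, or 70% (10.3). Non-completion: about 5%, 15 of 315 (5).

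**Assumptions.** f, the scan-failure share among all benign enrolled, is not given. I use 5% as the reference because it is the only planned figure, with 2% and 10% beside it. Failures are taken to be 70% benign like the rest, so 15 × 0.70 = 10.5, that is 10 or 11 benign failures and N = 220 or 221.

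**The plan's own figures.** The pass mark is the smallest r with P(X ≥ r | n, 0.30) ≤ 0.025.
- n = 83: r = 34, power at 45% = 80.18%.
- n = 210: r = 77, attained level 2.2%, power at 45% = 99.4%.

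Both powers match section 10.3.

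**Shift in the percentage.** With 210 valid benign scans, N = 210/(1-f). At 45% among valid scans the expected number spared is 0.45 × 210 = 94.5. All-enrolled share = 94.5/N:

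| f | N | Share |
|---|---|---|
| 2% | 214 | 44.2% |
| 5% | 221 | 42.8% |
| 10% | 233 | 40.6% |

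**Shift in the pass mark.** The same rule gives 80/220 (lower limit just above 30.0%) and 81/221 (30.3%).

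| Spared | Lower limit, of 210 | Lower limit, of 220 | Lower limit, of 221 |
|---|---|---|---|
| 77 | 30.1% | 28.7% | 28.6% |
| 79 | 31.0% | 29.6% | 29.4% |
| 80 | 31.5% | 30.0% (meets) | 29.9% |
| 81 | 32.0% | 30.4% (meets) | 30.3% (meets) |

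So 77 to 79 (10 failures) or 77 to 80 (11 failures) meet the bound on valid scans only. At f = 2% the band is 77 to 78; at f = 10% it is 77 to 84.

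**How likely this is.** With 11 failures, the chance of landing on 77 to 80 is about 2.0% if true valid-scan specificity is 45%, and about 22% if it is 38%. Suppose the all-enrolled share is exactly 30%. The valid-scan rate is then 0.30/(1-f), and the planned test passes with probability 3.5%, 6.7% or 17.0% at f = 2%, 5% or 10%.

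**At the planning value.** With the failures counted, power is 98.0% (80/220, true share 94.5/220) or 97.2% (81/221, true share 94.5/221).

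**Sensitivity runs the other way.** With 4 malignant failures kept as positive, 86/90 (lower limit 89.0%) becomes 90/94 (89.5%). Leaving them out is conservative there.

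**The case against.** The strongest reply is that the endpoint is defined on the combined conventional-imaging and DOT assessment, which needs a DOT result. Specificity conditional on a usable scan is a legitimate quantity, and section 7.1 words its reading as an indication of what might happen if NIR data were used. This stands as far as the hypothesis test goes. A reader might infer that a pass at 77/210 is a false pass, or that the primary analysis set has to be replaced. The documents support neither: 77/210 is a correct test of the hypothesis as defined. What remains is the label. Section 10.2 calls the same ratio the benign biopsy spare rate without that hedge.

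A reader might also take the 5% as a device-failure rate. Section 5 speaks of not completing the study, which can include withdrawal or a cancelled biopsy, and a biopsy result is not assured for those participants. With only 3 benign failures (N = 213) the pass mark is 78, and just one result, 77, changes side.

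Nor does the exclusion favour the device on every measure; on sensitivity it works against it. Counting every failed scan as positive would also misclassify BI-RADS 3 patients who chose biopsy, whom the plan treats as negative and tracks separately. Finally, restoring failed scans gives a rate for the enrolled population, not for all women sent for biopsy, since eligibility already excludes implants, superficial lesions and others.

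The exclusion itself is inferred from the wording on valid data, evaluable subjects and no imputation. The sections agree with one another, and if another rule is intended it is not written down.

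**Conclusion.** The point holds for specificity read as a spare rate. As written, the plan overstates the avoidable share by a factor of 1/(1-f): about 2 points at 45% and an assumed f of 5%, and about 1 to 4 points over 2% to 10%. A result of 77 to 79 or 80 of 210 would meet the 30% bound among valid scans and miss it among all enrolled benign cases. At the planned 45% the conclusion is unaffected, with power of 97 to 98%. The size rests on f, which the documents do not give, and on failures being benign in the same proportion as the rest. This should be corrected before results are known, but it does not undermine the planned specificity test.

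**What to change.** In section 10.4:

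1. Define evaluable, and keep the valid-scan specificity test as planned.
2. Report the number of participants without valid DOT data, separating failed or invalid scans from withdrawal and other non-completion.
3. Add a pre-specified analysis of all enrolled participants with a biopsy result, in which those without valid DOT keep their conventional-imaging assessment: BI-RADS 4A to 5 positive, BI-RADS 3 patients who chose biopsy tracked separately as section 7 already provides. This uses an observed assessment, so it does not conflict with the no-imputation rule.
4. Take any statement of the percentage of benign biopsies avoidable from that analysis, and align the wording in 7.1 and 10.2.
5. Give sensitivity, PPV and NPV on both sets.

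The cost is wording, one extra tabulation and a headline figure about 2 points lower at f = 5%. No added enrolment is needed.

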7. DATA COLLECTION AND ANALYSIS

Study specific data will be collected from subjects after informed consent is obtained. The following data may be collected on the patient questionnaire: demographic information (name, DOB, Age, Race and Hispanic or Non-Hispanic) MRN#, imaging reports (e.g. mammography, US, PET, MRI, etc.), core biopsy pathology reports, surgical pathology reports if available, breast cancer risk information, etc.

In some cases, the pathologist may review existing biopsy specimens with special staining to look for signs of increased blood supply and vessel density. This will not require additional slicing of standard of care biopsy specimens; thus, samples will not be labeled or stored for the research study. The results of these tests will not be placed in the patient medical record. The results of these tests may be given to the investigators to correlate to the results of the NIR/US procedures.

[figure not shown]
[name], specialist in breast pathology, will assess pathological findings.

The goal of this study is to assess the impact of adjunctive US-guided DOT on the accuracy of breast biopsy recommendations for abnormalities undergoing US-guided breast biopsy. In particular to assess the effect of combining US-guided DOT with CI to: 1. reduce the rate of benign breast biopsy, i.e. decrease false positive biopsy recommendations, and 2. to maintain sensitivity, i.e. maintain true positive recommendations.

Additional goals of this study are to assess the role of US-guided DOT in managing discordant biopsy results and assess the correlation of optical imaging parameters with the presence

and intensity of contrast enhancement of the abnormality undergoing biopsy in patients who have undergone CEM.

Figure 4 – Reader Study Design

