To accomplish the aims of assessing the impact of adjunctive US-guided DOT on reducing benign biopsy recommendation (i.e. FPs), while maintaining sensitivity (i.e. TPs) we will conduct a reader study of the 300 subject trial. Three of four study radiologists will serve as study readers for each case. (To eliminate potential bias a study radiologist performing the biopsy will not serve as a reader for that case.) As noted above the study radiologist who performs or supervises the US-guided DOT exam will be one of the readers. Two additional study radiologist readers will subsequently and independently review the available pre-existing patient information and CI data, (excluding the US-guided biopsy exam) and complete CI and DOT CRFs blinded to the pathology result of the abnormality that underwent biopsy. The CRFs include a BI-RADS assessment. The reader will first complete the CI CRF blinded to the US-guided DOT result, then after reviewing the optical data (tHB concentration and distribution) the reader will complete the DOT CRF including the impact of US-guided DOT information on the BI-RADS assessment, i.e. no change, decreased or increased.

Similar to the CI plus DOT workflow, for cases that have CEM, a CI CRF will be completed first, followed by a CEM specific CRF including a BI-RADS assessment and the impact of CEM on the BI-RADS assessment will be recorded. As noted above, the study radiologist that supervises the US-guided DOT and CEM exams will serve as one of the study readers. For the subsequent two readers we will alternate which adjunctive modality (i.e. CEM or US-DOT) is reviewed first and separate the subsequent review of the second adjunctive modality by a minimum of 4 weeks to prevent recollection bias).

Figure 4 diagrams the core analysis. Combined CI and US-guided DOT BI-RADS 2 and 3 assessments will be considered test negative, and BI-RADS 4A, 4B, 4C, and 5 assessments will be considered test positive. For negative tests, the biopsy proven malignant group (Gc, see Fig. 1(b)) represents false negative results, and the benign group Gd represents true negatives and reflects the potential reduction in benign biopsy recommendation if US-guided DOT were used as SOC. Ga represent true positives and Gb represent false positives utilizing adjunctive US-guided DOT. A comparison of the Ga groups i.e. CI alone vs. CI & DOT will constitute the assessment of the effect of adjunctive US-guided DOT on sensitivity.

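### The exploratory ROC and tree modelling in section 10.4 leaves out the conventional-imaging BI-RADS, so its AUC cannot show what measured tHb adds to conventional imaging

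*Combined protocol and SAP*

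**What the plan says.** Section 7 sets the question as one of added value. The trial is to "assess the effect of combining US-guided DOT with CI", with the aim of fewer benign biopsies at maintained sensitivity. Section 1.1 places the main intended use in BI-RADS 4A and 4B lesions, where a low tHb may support a downgrade.

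The reader study in section 7 collects what is needed to study this. Three radiologists read each case, and "The reader will first complete the CI CRF blinded to the US-guided DOT result". Each then records a BI-RADS assessment with the optical data in view. On sensitivity, "A comparison of the Ga groups i.e. CI alone vs. CI & DOT will constitute the assessment".

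Section 10.4 first gives the exact tests for specificity and sensitivity. It then turns to exploration, meant to refine the classification algorithm and the tHb cut-off. There "ROC analysis will evaluate the quantitatively measured tHb for pathological results of malignant biopsies", and "other parameters (such as oxyHb, deoxyHb, and distributions) will be either linearly incorporated with tHb to maximize the ultimate area under ROC", or else entered in a classification tree. Finally, "The area under the ROC will be calculated to gauge the model's overall discriminative ability for biopsy results". Every predictor named is optical. No AUC for CI alone, no AUC for CI plus tHb and no ROC within BI-RADS groups is planned.

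**The concern.** Eligibility runs from BI-RADS 3 to 5, a scale built to rank the suspicion of malignancy. An AUC taken across that range credits tHb for ranking a BI-RADS 5 cancer above a benign 4A lesion, which the radiologist has already done without it. A marker that only follows what CI shows will therefore discriminate in the pooled data while adding nothing to the CI assessment.

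What is at stake is the interpretation of an exploratory result. The decision DOT is meant to change is made among lesions with similar CI assessments. The planned AUC cannot distinguish a tHb that helps there from one that repeats the category. A cut-off refined on the pooled data may also not suit the 4A and 4B lesions it is meant for.

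**Working it through.** **The plan's own figures.** The documents give no AUC target, precision or sample size for the ROC analysis, so there is nothing to reproduce for it. The exact-binomial powers in section 10.3 do reproduce (80.18% with 83 benign, 99.4% with 210 benign, 89.33% with 90 malignant), but they do not bear on this point.

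**Inputs, all assumed.** The documents give no BI-RADS mix, no malignancy rate by category and no association between tHb and BI-RADS. BI-RADS 3 is left out of the illustration because the plan tracks it separately.

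| Category | Share | Malignant | Malignant per 300 | Benign per 300 |
|---|---|---|---|---|
| 4A | 45% | 8% | 10.8 | 124.2 |
| 4B | 30% | 25% | 22.5 | 67.5 |
| 4C | 12% | 55% | 19.8 | 16.2 |
| 5 | 13% | 92% | 35.9 | 3.1 |

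Overall malignancy is 0.036 + 0.075 + 0.066 + 0.1196 = 29.7%, close to the planned 90/300. tHb is taken as normal with SD 1 and a mean that rises s SD per category. Within a category it is unrelated to malignancy.

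**Formula.** Take a random malignant and a random benign lesion, and let d be the malignant lesion's category minus the benign lesion's category, in steps. Then pooled AUC = Σ w(d) Φ(d·s/√2), where w(d) is the share of pairs with difference d. From the table:

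| d | −3 | −2 | −1 | 0 | 1 | 2 | 3 |
|---|---|---|---|---|---|---|---|
| w(d) | 0.0018 | 0.0131 | 0.0615 | 0.1754 | 0.2510 | 0.2600 | 0.2373 |

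For s = 0.5 the terms are 0.0003 + 0.0031 + 0.0223 + 0.0877 + 0.1602 + 0.1977 + 0.2030 = 0.674.

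| s (SD per step) | 0 | 0.1 | 0.25 | 0.5 | 0.75 | 1.0 |
|---|---|---|---|---|---|---|
| Pooled tHb AUC | 0.50 | 0.54 | 0.595 | 0.674 | 0.731 | 0.767 |

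The AUC inside every category is 0.50 by construction. BI-RADS alone, with ties counted as one half, gives 0.2510 + 0.2600 + 0.2373 + 0.1754/2 = 0.836.

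**Why the pooled figure misses the decision.** Under these inputs 62.6% of cancers are in 4C or 5 and 90.8% of benign lesions are in 4A or 4B. Pairs with both lesions in 4A/4B make up only 0.374 × 0.908 = 34% of those behind the AUC.

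**Other assumed mixes.** Three mixes that include BI-RADS 3, with 32% malignant overall, gave a pooled tHb AUC of 0.59 to 0.81 for 0.25 to 1.0 SD per step, and 0.84 to 0.89 for BI-RADS alone. In 1,000 simulated trials of 300 lesions at each of 0.5, 0.75 and 1.0 SD per step (one of these mixes), the pooled AUC differed significantly from 0.5 every time. A logistic test of tHb adjusted for BI-RADS was significant in 4 to 6% of trials, about the nominal 5%.

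**Precision of subgroup AUCs.** Near AUC 0.5 the 95% half-width is 1.96·√[(n₁+n₀+1)/(12·n₁·n₀)]. The table gives 0.18 (4A), 0.14 (4B), 0.19 (4C) and 0.34 (5). For 4A and 4B pooled, n₁ = 33.3 and n₀ = 191.7, so the half-width is 1.96·√[226/(12 × 33.3 × 191.7)] = 0.11.

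**The case against.** The strongest reply is that this ROC is not the plan's test of added value. It is exploratory, no success rule or sample size depends on it, and the AUC is described only as a measure of overall discrimination. Success rests on the confidence limits for specificity and sensitivity of the readers' combined CI plus DOT assessment. All of this stands, and it limits the weight of the point.

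A reader might infer that the trial never assesses adjunctive use. The documents do not support that: readers assess CI first and then CI with DOT, and the formal endpoints use the combined call. Those endpoints do not, however, isolate what the measured tHb value adds to the CI category, since they depend on how readers use it.

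A reader might also take the ROC to be the only quantitative analysis of tHb. It is not. Section 10.4 also compares optical values in benign 4C/5 lesions with those in malignant lesions, and correlates tHb with enhancement on CEM. Neither asks what tHb adds given CI BI-RADS: the first restricts only its benign group by category, and the second does not adjust for it.

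The size is assumed throughout. If tHb is unrelated to BI-RADS the problem vanishes, and section 1.1 gives some reason to expect only partial overlap, since focal fibrosis can look highly suspicious on ultrasound yet have low tHb. This argues for measuring the overlap, which the plan as written does not do.

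Finally, section 10.4 does not say outright that the ROC pools all categories, and its list of parameters is open-ended. Adding BI-RADS is therefore permitted, but it is not planned, and no restriction by category is stated.

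**Conclusion.** The point holds for the exploratory ROC and classification modelling in section 10.4, and only there. As written, its AUC cannot show whether measured tHb carries information beyond the CI assessment. Under the assumed mix, a tHb with no such information would reach 0.54 to 0.77 for 0.1 to 1.0 SD per BI-RADS step, against 0.84 for BI-RADS alone. These figures show the mechanism and do not predict this trial's result. Nor do they support the inference that tHb adds nothing: the documents do not settle that either way. The conclusions on specificity and sensitivity are untouched. The change is worth making because the baseline assessment is already recorded and the better analysis costs almost nothing.

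**What to change.** In section 10.4, before the ROC analysis is run:

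- Fit malignancy on pre-DOT CI BI-RADS alone, then on CI BI-RADS plus tHb, then with the other optical parameters added.
- State in advance how the three readers' CI BI-RADS values enter, for example as reader-level data with standard errors clustered by patient, or as the median category.
- Report the BI-RADS-adjusted tHb effect, and the change in AUC with a confidence interval. Correct the AUCs for optimism by bootstrap or cross-validation, resampling patients, because the combination is chosen to maximise AUC on the same data.
- Show the tHb AUC in the pooled 4A/4B group as descriptive (half-width about 0.11 under the assumed mix). Do not report it for each single category, where it would be too imprecise. The pooled 4A/4B figure still contains the 4A-to-4B difference, so it supplements the adjusted analysis and does not replace it.
- Offer CI BI-RADS as a candidate in the tree model, and keep the unadjusted tHb AUC as descriptive.

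The cost is a few lines of SAP text and code and a little more analysis work, with no new data. The downside for the sponsor is a less favourable-looking figure if tHb overlaps with BI-RADS.
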